7.1.6.2. Depression Assessment

The PROMIS Pediatric SF v2.0 and the PROMIS Parent Proxy SF v2.0 will be used during the study to monitor participants for depression ([Yount 2019](#)). The PROMIS Pediatric SF v2.0 is self-administered and the PROMIS Parent Proxy SF v2.0 is completed by the parent of a child in the study, to assess for symptoms of depression. The assessment consists of 8 items using multiple choice response format and will be used at screening and all subsequent visits specified.

Refer to [Section 6.1.6](#) for depression and/or anxiety individual treatment-stopping criteria.

7.1.6.3. Anxiety Assessment

The PROMIS Pediatric Anxiety SF v2.0 and the PROMIS Parent Proxy Anxiety SF v2.0 will be used during the study to monitor participants for anxiety. The Pediatric version is self-administered and the PROMIS Parent Proxy SF v2.0 is completed by the parent of a child in the study to assess for symptoms of anxiety. The assessment consists of 8 items using a multiple-choice response format and will be used at screening and all subsequent visits specified.

Refer to [Section 6.1.6](#) for depression and/or anxiety individual treatment-stopping criteria.

7.1.6.4. Survey of Well-Being of Young Children

The SWYC is a brief questionnaire (completed by parents) that assesses the following 3 categories of well-being in children 2 to 4 years of age: developmental, emotional/behavioral, and family.

Refer to [Section 6.1.6](#) for depression and/or anxiety individual treatment-stopping criteria.

7.2. Adverse Events and Serious Adverse Events

7.2.1. Definition of Adverse Event

An AE is any untoward medical occurrence in a participant participating in a clinical trial. Examples of AEs include but are not limited to:

- Clinically significant abnormal test results
- Clinically significant symptoms and signs
- Changes in physical examination findings
- Hypersensitivity
- Progression/worsening of underlying disease

A TEAE is defined as an AE that occurs during or after administration of the first dose of study drug until 30 days after the final dose of study drug (Safety Follow-up Visit). For AEs that occur on the date of the first dose of study drug, the time of onset (before or after intake of study drug) must be specified.

An abnormal test result should be reported as an AE if any of the following criteria are met:

- It is associated with accompanying symptoms
- It requires additional diagnostic testing or medical/surgical intervention
- It leads to a change in study drug dosing or study drug discontinuation, significant additional concomitant drug treatment, or other therapy
- It is considered to be an AE by the Investigator or Sponsor

Merely repeating an abnormal test, in the absence of any of the above conditions, does not constitute an AE. Any abnormal test result that is determined to be an error does not require reporting as an AE.

Examples of events that do not meet the definition of an AE include but are not limited to:

- Clinically significant abnormal test result or other abnormal safety assessment associated with the underlying disease, unless it is more severe than expected for the participant's condition
- The underlying disease and its signs and symptoms, unless they are more severe than expected for the participant's condition
- Medical and surgical procedures; the condition that leads to the procedure is the AE if it meets the definition of an AE. For example, an acute appendicitis that begins during the AE reporting period should be reported as the AE, and the resulting appendectomy should be recorded as treatment for the AE
- Anticipated day-to-day fluctuations of pre-existing disease(s) or condition(s) present or detected at the start of the study that do not worsen.

7.2.2. Definition of Serious Adverse Event

An SAE or serious adverse drug reaction is any untoward medical occurrence at any dose that meets any of the following criteria:

- Results in death
- Is life threatening (immediate risk of death)
- Requires inpatient hospitalization or prolongation of existing hospitalization
- Results in persistent or significant disability/incapacity
- Is a congenital anomaly/birth defect
- Is an important medical event

Medical and scientific judgment should be exercised in determining whether an event is an important medical event. An important medical event may not be immediately life threatening and/or result in death or hospitalization. However, if it is determined that the event may jeopardize the participant and may require intervention to prevent one of the other outcomes listed in the definition above, the important medical event should be reported as serious. Examples of such events include allergic bronchospasm that requires intensive treatment in an emergency room or at home, blood dyscrasias or convulsions that do not result in hospitalization, or the development of drug dependency or drug abuse. If either the Sponsor or the Investigator believes that an event is serious, the event must be considered serious and evaluated by the Sponsor for expedited reporting.

Hospitalization does not include rehabilitation, hospice, or skilled nursing facilities; respite care; nursing homes; observation in an Emergency Department of Acute Care center, or same-day surgeries (as outpatient/same day/ambulatory procedures).

Hospitalization or prolongation of hospitalization in the absence of a precipitating clinical AE is not in itself an SAE. Examples include the following:

- Admission for treatment of a pre-existing condition not associated with the development of a new AE or with a worsening of the pre-existing condition (e.g., for workup of persistent pre-treatment lab abnormality)
- Social admission (e.g., participant has no place to sleep)
- Administrative admission (e.g., for yearly physical exam)
- Protocol-specified admission during a clinical trial (e.g., for a procedure required by the trial protocol)
- Optional admission not associated with a precipitating clinical AE (e.g., for elective cosmetic surgery)
- Pre-planned treatments or surgical procedures should be noted in the baseline documentation for the entire protocol and/or for the individual participant.

7.2.3. Classification of an Adverse Event

The Investigator must record all AEs in the eCRF with information about:

- Duration (start and end dates)
- Severity ([Section 7.2.3.1](#))
- Relationship to study drug ([Section 7.2.3.2](#))
- Action(s) taken and, as relevant, the outcome ([Section 7.2.3.3](#) and [Section 7.2.3.4](#))
- Seriousness ([Section 7.2.2](#))

7.2.3.1. Severity

The Investigator will assess the severity of each AE according to the National Cancer Institute CTCAE version 5.0 ([CTCAE 2017](#)), which is summarized in [Table 5](#).

Table 5. Severity of Adverse Events

Grade 1: Mild; asymptomatic or mild symptoms; clinical or diagnostic observations only; intervention not indicated.
Grade 2: Moderate; minimal, local, or noninvasive intervention indicated; limiting age-appropriate instrumental ADL (preparing meals, shopping for groceries or clothes, using the telephone, managing money, etc.).
Grade 3: Severe or medically significant but not immediately life threatening; hospitalization or prolongation of hospitalization indicated; disabling; limiting self-care ADL (bathing, dressing and undressing, feeding self, using the toilet, taking medications, and not bedridden).
Grade 4: Life-threatening consequences; urgent intervention indicated.
Grade 5: Death related to AE.

Abbreviations: ADL=activities of daily living; AE=adverse event.

Note the distinction between the severity and the seriousness of an AE. A severe event is not necessarily a serious event. Severe is a category used for rating the intensity of an event, and both AEs and SAEs can be assessed as severe. For example, a headache may be severe (interferes significantly with participant's usual function) but would not be classified as serious unless it met at least one of the criteria for an SAE listed in [Section 7.2.2](#), such as resulting in hospitalization.

If there is a change in the severity of an ongoing AE, it will be recorded as part of the same event, with the worst grade of severity for the entire event timeframe being recorded.

7.2.3.2. Relationship to Study Drug

The Investigator will assess the relationship of each AE to study drug according to the categories in [Table 6](#). This assessment will serve to determine whether there exists a reasonable possibility that the study drug caused or contributed to the AE.

Table 6. Relatedness of Adverse Event to Study Drug

UNRELATED: This category applies to those AEs that are clearly and incontrovertibly due to extraneous causes (disease, environment, etc.).
UNLIKELY RELATED: This category applies to those AEs that are judged to be unrelated to the study drug but for which no extraneous cause may be found. An AE may be considered unlikely to be related to the study drug if or when it meets two of the following criteria : (1) it does not follow a reasonable temporal sequence in relation to administration of the study drug; (2) it could readily have been produced by the participant's clinical state, environmental or toxic factors, or other therapies administered to the participant; (3) it does not follow a known pattern of response to the study drug; or (4) it does not reappear or worsen when the study drug is re-administered.
POSSIBLY RELATED: This category applies to those AEs for which a connection to study drug administration cannot be ruled out with certainty. An AE may be considered possibly related if or when it meets two of the following criteria : (1) it follows a reasonable temporal sequence in relation to administration of study drug; (2) it could not readily have been produced by the participant's clinical state, environmental or toxic factors, or other therapies administered to the participant; or (3) it follows a known pattern of response to the study drug.
PROBABLY RELATED: This category applies to those AEs that the Investigator thinks are related to the study drug with a high degree of certainty. An AE may be considered probably related if or when it meets three of the following criteria : (1) it follows a reasonable temporal sequence in relation to administration of the study drug; (2) it could not be reasonably explained by the known characteristics of the participant's clinical state, environmental or toxic factors, or other therapies administered to the participant; (3) it disappears or decreases on cessation or reduction in dose of study drug. There are exceptions when an AE does not disappear upon discontinuation of the study drug yet drug-relatedness clearly exists (e.g., as in bone marrow depression, fixed drug eruptions, or tardive dyskinesia); or (4) it follows a known pattern of response to the study drug.
DEFINITELY RELATED: This category applies to those AEs that the Investigator thinks are incontrovertibly related to the study drug. An AE may be assigned an attribution of definitely related if or when it meets all of the following criteria : (1) it follows a reasonable temporal sequence in relation to administration of the study drug; (2) it could not be reasonably explained by the known characteristics of the participant's clinical state, environmental or toxic factors, or other therapies administered to the participant; (3) it disappears or decreases upon cessation or reduction in dose of study drug and recurs with re-exposure to the study drug (if rechallenge occurs); and (4) it follows a known pattern of response to the study drug.

Abbreviation: AE=adverse event.

The Investigator will use clinical judgment and consult the IB to determine the relationship. Alternative causes, such as underlying disease(s), concomitant therapy, and other risk factors, as well as the temporal relationship of the event to study drug administration will be considered and investigated.

AEs classified as unrelated or unlikely related will be considered not related to treatment, and AEs classified as possibly, probably, or definitely related will be considered related to treatment.

7.2.3.3. Action Taken

The action taken with the study drug in response to an AE must be classified as one of the following:

- No change (study medication schedule maintained or no action taken)
- Study medication interrupted
- Study medication discontinued.

AEs requiring therapy must be treated with recognized standards of medical care to protect the health and well-being of the participant. If medication is administered to treat the AE, this medication should be recorded.

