3.1.3. Extension Period

Participants who complete the 12- or 4-week treatment period, depending on cohort, may be eligible to continue dosing to complete 2 years on treatment in an extension study. Participants will sign a separate informed consent form at Week 12 or Week 4. Pending DMC review, participants in Cohorts 1 and 1a (if indicated) will receive the adult equivalent dose of 200 mg QD during the extension (i.e., Cohort 1 participants will immediately switch to 200 mg equivalent if the DMC has already recommended this dose for Cohort 2, or participants may enter the extension period on 50 mg equivalent and increase to 200 mg equivalent after such a recommendation is made). If a Cohort 1-3 participant is to dose escalate to the 200 mg equivalent, they may do so at the next scheduled visit or come to the clinic for an unscheduled visit and pick up their new supply of study drug. Participants will receive a follow-up phone call 2 weeks after dose escalation to check for AEs.

Further tildacerfont dose adjustments may occur during the extension on a case-by-case basis at the discretion of the Investigator with Sponsor approval. Any extension participant may receive the highest dose recommended by the DMC for their age group. Dose changes (increase or decrease) may occur at a scheduled visit, an unscheduled visit, or via a phone visit, but any dose escalation > 200mg QD will be followed by safety labs (link to list) within 2-4 weeks of the change. Once all participants are in the extension period, safety- data will be reviewed every 6 months by the DMC. Weight-based dose adjustments may be made at any extension visit, with no follow-up labs required.

For Cohorts 1-3, the first visit of the extension will be Week 12. For Cohorts 4-9, Week 4 will be the first extension visit, followed by extension clinic visits at Weeks 8 and 12 (\pm 2 weeks). Starting at Week 12, all participants will attend clinic visits every 12 weeks (\pm 2 weeks).

Approximately a 12-week supply of study drug, as appropriate, will be dispensed at each visit. Approximately 30 days after the last dose of study drug, participants will have a final follow-up visit conducted by telephone. Concomitant medications and AEs will be reviewed. If any ongoing safety issues are identified, the participant may be asked to visit the clinic for additional tests, labs, or assessments.

The extension study visits will include the following:

- Review concomitant medications for any changes

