6.1.8. Dose Limiting Toxicity

If 2 participants in a cohort meet individual stopping criteria, the entire cohort will be stopped or dose-reduced.

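### The adverse-event action-taken field has no code for a reduced dose, so an AE that lowers the dose, mainly in the extension, loses its link to that reduction

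*Protocol*

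**What the plan says.** Protocol 7.2.3.3 introduces the field with "The action taken with the study drug in response to an AE must be classified as one of the following". Three categories follow. The first is no change, explained as the schedule being kept or nothing being done. The others are "Study medication interrupted" and "Study medication discontinued". There is no category for a reduced or changed dose, no other, and no not applicable.

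Elsewhere the documents provide for a lower dose or presuppose one:

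- Protocol 3.1.3, on the extension: "Dose changes (increase or decrease) may occur at a scheduled visit, an unscheduled visit, or via a phone visit". Further adjustments are case by case, at the Investigator's discretion with Sponsor approval.
- Protocol 6.1.8, repeated in SAP 5.3.1.8: "If 2 participants in a cohort meet individual stopping criteria, the entire cohort will be stopped or dose-reduced".
- Protocol 7.2.1 gives as one reason for reporting an abnormal test result as an AE: "It leads to a change in study drug dosing or study drug discontinuation".
- Protocol 7.2.3.2, Table 6, uses improvement after the dose is stopped or lowered as a criterion for probable and definite relatedness.

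SAP 5.3.1.1 says that action taken is recorded and adds no categories. SAP 14.1 plans a separate listing and a summary line for TEAEs leading to discontinuation. It plans nothing for TEAEs leading to reduction or interruption.

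**The concern.** The list is closed: one of three codes must be used. If an investigator lowers a participant's dose because of an AE, the schedule has not been maintained, dosing has not been interrupted and drug has not been stopped. Any of the three codes misdescribes what happened.

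AEs and SAEs are the primary endpoint of both treatment periods and of the extension (Protocol Section 2). Extension participants may receive the highest dose recommended by the DMC for their age group and may complete two years on treatment (3.1.3). A reduction made because of an AE is direct information on tolerability short of stopping, and this field is where it should be recorded. Table 6 also asks investigators to weigh the response to a lower dose, which is an action that the AE record cannot hold.

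**Working it through.** No figure in the plan bears on this, so there is nothing to recompute. The check sets the three codes against each place where the documents allow or mention a lower dose, and then asks whether another planned output would recover the link.

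**Count.** There are three codes, and none covers a reduction. Two provisions allow a lower dose (3.1.3 and 6.1.8). Two more places presuppose a dosing change or a reduction (7.2.1 and Table 6).

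**Where the gap can bite.**

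1. *Individual rules.* The rules in Protocol 6.1.1 to 6.1.6 (DLT, liver chemistry, QT, suicidality, depression or anxiety) hold or discontinue drug, and 6.1.7 speaks of considering discontinuation. The codes for interrupted and discontinued fit. The dose adjustment scheduled in the 12-week and 4-week periods is weight-based (3.1.2.4, Appendices 1 and 3). No section provides for an AE-driven reduction in an individual during those periods.
2. *Cohort rule.* This is triggered when two participants meet individual stopping criteria. Protocol 6.1 discontinues drug in such participants, so the triggering AEs have a correct code.
3. *Extension.* Decreases are allowed for individuals at the Investigator's discretion. An AE-driven decrease here has no correct code, and this is the main exposure to the gap.

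**Whether the link can be recovered elsewhere.**

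1. Reasons are to be listed and summarized for discontinuations only (Protocol 8.3.4.1, SAP 11.1).
2. The exposure listing holds tablet counts, nominal dose and dose per kg, with no reason for a change (SAP 12.1). SAP Section 15 drops the exposure summary because of limits in the exposure and accountability data.
3. Extension doses may also change for weight or efficacy (Protocol 3.1.3, Appendix 4). A lower dose in the dosing record therefore does not show that an AE caused it.
4. SAP 14.1 selects on discontinuation only.

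No planned output restores the connection between the AE and the reduction.

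**AEs with no drug action possible.** AEs are recorded from consent (Protocol 7.2.4) and until about 30 days after the last dose (SAP 5.3.1.1). Before the first dose and after the last there is no dosing to change, yet one of the three codes is still required.

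**The case against.** The strongest reply is that the list matches the individual safety rules, which only hold or discontinue. That is right for the main treatment periods, and it confines the point largely to the extension. Even there, 3.1.3 does not tie decreases to AEs, and a separate SAP will cover the extension (SAP Section 4). Protocol 7.2.1 is weak support by itself: its criterion concerns abnormal test results, and an interruption is also a change in dosing. All of this stands and reduces the size of the point. It does not remove it, because 3.1.3 leaves the reason for a decrease open and the required list cannot record one made for an AE. Deferral to another SAP does not mend the field, and SAP Table 3 still refers extension AEs to 14.1.

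A reader might infer more than the documents support:

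- *That the AEs behind a cohort dose reduction have no code.* They do, as those participants are discontinued under 6.1. The other participants' doses would fall under a cohort rule, not in response to their own AEs, so no change can be accurate for those AEs.
- *That such AEs would be hidden from the DMC and the tables.* All reported AEs are listed, and TEAEs are tabulated by dose level and cohort (SAP 14.1). The DMC reviews available data throughout (Protocol 3.1.1) and, once all participants are in the extension, reviews safety data every six months (3.1.3).
- *That every AE-driven reduction has been miscoded and past records need re-coding.* SAP Section 2 cites case report forms v7.0, which are not among the documents and may carry more options. No AE-driven reduction is documented.

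**Conclusion.** The point holds in a narrow form. As written, Protocol 7.2.3.3 gives no correct code for an AE that leads to a lower dose, although the protocol allows lower doses and uses the response to them in judging causality. The practical gap lies mainly in individual decreases during the extension. The primary endpoint counts are unaffected: one attribute of the AE is wrong, and its link to the reduction is not recoverable from the planned outputs. The number of AEs affected is unknown and could be zero.

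This rests on two assumptions: that sites follow the protocol list as written, and that the AE eCRF offers no further option. If the eCRF already has a code for dose reduced, what remains is a wording mismatch and a missing listing. It is a minor point, worth fixing because the change is cheap. It takes no position on when a dose should be lowered.

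**What to change.** Reconcile Protocol 7.2.3.3 with 3.1.3, 6.1.8, 7.2.1 and Table 6:

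- Add dose reduced to the list in 7.2.3.3, and not applicable for AEs before the first or after the last dose.
- Check the AE eCRF and add the same codes if they are not already there.
- In SAP 14.1 and in the separate extension SAP, list TEAEs leading to dose reduction or to interruption beside those leading to discontinuation.

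The cost is a short protocol and SAP edit, one listing and, if needed, a small eCRF update. If the eCRF proves to lack the code, check whether any AE has already been followed by a dose decrease; only such records would need correcting. Nothing changes in dosing, visits or sample size.

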7.2.3.4. Outcome

The outcome of each AE will be recorded as one of the categories in [Table 7](#).

Table 7. Outcome of Adverse Events

Not recovered/not resolved: The event has not improved or recuperated.
Recovered/resolved: The event has improved or recuperated. The participant recovered from the AE. Record the AE stop date.
Recovering/resolving: The event is improving. No AE stop date should be recorded when an AE is recovering/resolving.
Recovered/resolved with sequelae: The participant recuperated but retained pathological conditions resulting from the prior disease or injury. Record the AE stop date. The AE stop date will represent the date the AE stabilized with no change in event outcome anticipated.
Unknown: There is an inability to access the participant/guardian or the participant's records to determine the outcome (i.e., participant/guardian withdraws consent or is lost to follow-up). No AE stop date should be recorded.
Fatal: The AE directly caused death. Record the date of death as the AE stop date.

Abbreviation: AE=adverse event.

